6.8.1 Primary Efficacy Analysis

The primary efficacy endpoint is the proportion of patients with A1C $< 7.0\%$ at Week 24 and no episode of SH and no episode of DKA from randomization to Week 24. The analysis of this endpoint will be based upon the mITT population. The frequency and percentage of patients with A1C $< 7.0\%$ at Week 24 and no episode of SH or episode of DKA from randomization to Week 24 will be presented by treatment group. For this endpoint, only positively adjudicated SH and DKA events will be assessed over the cumulative randomized 24-week Double-blind Treatment Period. The cut-off dates for the inclusion of SH and DKA events, along with other EOSIs, are described in detail in [Section 6.9.2](#). In brief, the cut-off date is the date of the last dose of double-blind study drug for SH events and 30 days after the date of the last dose of study drug for DKA.

Analysis of the primary efficacy endpoint at Week 24 will be performed using the CMH test and 95% CLs based on normal approximation methods with a continuity correction factor, as described in [Section 6.8](#) for binary efficacy endpoints. The individual components of the endpoint will be summarized separately using descriptive methods. Each of these components will be expressed as a binomial proportion: proportion of patients with A1C $< 7.0\%$ at Week 24, proportion of patients with no episodes of DKA from randomization to Week 24, and proportion of patients with no episodes of SH from randomization to Week 24.

Bar charts displaying proportions of patients with A1C $< 7.0\%$ at Week 24 and no episode of SH or episode of DKA will be presented from randomization to Week 24 by treatment groups.

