10.3 Study Endpoints

10.3.1 Efficacy Endpoints

10.3.1.1 Primary Efficacy Endpoint

The primary endpoint is to demonstrate the superiority of sotagliflozin 400 mg versus placebo in the proportion of patients with A1C $< 7.0\%$ at Week 24 and no episode of severe hypoglycemia and no episode of DKA after randomization when used as an adjunct in normal weight and overweight/obese adult patients with T1D who have inadequate glycemic control with insulin therapy.

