3 EFFICACY AND SAFETY VARIABLES

3.1 Efficacy Endpoints

3.1.1 Primary Efficacy Endpoint

The primary endpoint is to demonstrate the superiority of sotagliflozin 400 mg versus placebo in the proportion of patients with A1C <7.0% at Week 24 and no episode of SH and no episode of DKA after randomization when used as an adjunct in normal weight and overweight/obese adult patients with T1DM who have inadequate glycemic control with insulin therapy.

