6.8.6 Net Clinical Benefit

Summaries for the following net clinical benefit endpoints assessed at the end of Double-blind Treatment Period will be provided for each treatment group in the mITT population:

- A1C at Week 24 <7.0% and SH
- A1C at Week 24 <7.0% and no SH
- A1C at Week 24 <7.0% and DKA
- A1C at Week 24 <7.0% and no DKA
- A1C at Week 24 <7.0% and no weight gain
- A1C at Week 24 <7.0% and weight gain >5%
- A1C at Week 24 <7.0% and weight loss >5%
- A1C at Week 24 <7.0% and bolus insulin reduction $\geq 20\%$
- A1C at Week 24 <7.0% and bolus insulin reduction $\geq 30\%$
- A1C at Week 24 <7.0% and basal (or non-bolus) insulin reduction $\geq 20\%$
- A1C at Week 24 <7.0% and basal (or non-bolus) insulin reduction $\geq 30\%$
- A1C at Week 24 <7.0% and total insulin reduction $\geq 20\%$
- A1C at Week 24 <7.0% and total insulin reduction $\geq 30\%$
- A1C at Week 24 <7.0% and no SH and no weight gain
- A1C at Week 24 <7.0% and no SH and no DKA and no weight gain

Only positively adjudicated SH and DKA will be included in these summaries, and the cut-off dates for their inclusion are defined in [Section 6.9.2](#). Similar summaries will be presented for other net clinical benefit measures at Week 24: A1C reduction of at least 0.3%, 0.4%, and 0.5%, with the associated SH, DKA, weight gain, and insulin reduction benefit categories. Exceptions are the summaries for A1C reduction of at least 0.4% and no weight gain; A1C reduction of at least 0.5% and no SH; and A1C reduction of at least 3% and bolus insulin reduction $\geq 20\%$, as these are either identical or very similar to 3 other efficacy endpoints (see [Section 6.8.4.4](#) to [Section 6.8.4.6](#)).

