Other AEs may be determined to be of special interest. EOSIs will be captured from first dose of double-blind study drug until 30 days after last dose of study drug. The following EOSIs may be attributed to the long-term effects of study drug: CV events (including death), bone fractures, venous thrombotic events, DILIs, and malignancies. In case any of these events is spontaneously reported by a patient, the event may be included in the analysis even if the onset is 30 days after last dose of study drug. Other EOSIs, excluding hypoglycemic events, will be included in the analysis if the onset is within 30 days of last dose of study drug. For a hypoglycemic event, the date of the last dose of double-blind study drug will be the cut-off date, regardless of the time of the hypoglycemic event; that is, a hypoglycemic event that occurs on the same day as the day of the last dose of double-blind study drug will be included in the analysis, even if it occurs at a time later than the last dose.

Events of special interest that will require adjudication by CEC are: MACE and specific CV events, DILIs, DKA (including all events of metabolic acidosis), and SH; EOSIs of SH, DKA, and CV events, if reported prior to randomization as SAEs, will be adjudicated as well.

An overall summary of number and percentage of patients with any Investigator-determined EOSIs will be presented by treatment group and overall for the Safety population. An overall summary of positively

Statistical Analysis Plan

Version: Final 1.0

Lexicon Pharmaceuticals Protocol No. LX 4211.1-312-T1DM

Date of Issue: 17 MAR 2017

Covance Study ID: 000000145143

adjudicated EOSIs will also be presented by treatment group. The summaries of Investigator-determined and positively adjudicated EOSIs will also be presented by use of CSII at Screening (Yes, NO).

Additional overall summaries will be presented for Investigator-determined EOSIs and positively adjudicated EOSIs, separately, for each of 3 time periods described as follows:

- EOSIs which start on or after the date and time of first dose of double-blind study drug and up to 30 days after the date of last dose
- EOSIs which start on or after the date and time of first dose of double-blind study drug and up to and including the date of last dose
- EOSIs which start after the date of last dose and up to 30 days after the date of last dose.

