Hypoglycemia will be summarized as the incidence of patients (%) with at least 1 hypoglycemic event, number of hypoglycemic events per patient per year of exposure, and the number of hypoglycemic events per patient per day, by treatment group, separately for the Baseline Period (ie., 2-week placebo Run-in Period), Double-blind Treatment Period (including only those events that occur between date and time of first dose and date of last dose of double-blind study drug) and Follow-up Period (including only those events that occur after the date of last dose of double-blind study drug and on or before the 30-Day Follow-up). The incidence rate of nocturnal hypoglycemic events by time, nocturnal hypoglycemic events by sleep status, and diurnal hypoglycemic events will be presented. Similarly, total documented hypoglycemia (symptomatic and asymptomatic), documented symptomatic hypoglycemia, documented asymptomatic hypoglycemia, total hypoglycemic events (ie, SH or documented hypoglycemia), SH events, and positively adjudicated SH events will be summarized.

Incidence rates of positively adjudicated SH events by treatment group and use of CSII at Screening (Yes, No) will be presented for the Double-blind Treatment Period.

Change from Baseline in hypoglycemic events calculated as a daily average over the week prior to the visit will be analyzed as a continuous variable as described in [Section 6.8.4.12](#). Since these data also serve as a measure of safety, additional analyses will be conducted. The first analysis of hypoglycemic events will be conducted using CMH tests stratified by the randomization factors at each clinic visit. These tests will provide inferential and descriptive summaries of the relative risk estimate for each of the 2 hypoglycemic event definitions: ≤ 70 mg/dL and ≤ 55 mg/dL by SMBG. The patient incidence of these hypoglycemic events will be counted over the week prior to the scheduled clinic visit used in the analysis. The second analysis of these data will examine the relative risk for each of the hypoglycemic event definitions over the entire Double-blind Treatment Period by use of a generalized linear model (GLM). The GLM will include fixed, categorical effects of treatment; BMI at Screening (< 25 kg/m², ≥ 25 kg/m²), Week -2 A1C ($\leq 9\%$, $> 9\%$), use of CSII at Screening (Yes, No), and an offset term for ~~treatment duration~~

Statistical Analysis Plan

Version: Final 1.0

Lexicon Pharmaceuticals Protocol No. LX 4211.1-312-T1DM

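### SAP 6.8.1 names the primary endpoint as running to Week 24 but counts SH only to last dose and DKA only to last dose + 30 days; for patients stopping more than 30 days before Week 24, no planned analysis of it counts both events to Week 24

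*SAP*

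**What the plan says.** **The endpoint as named.** Protocol 10.3.1.1 asks for "no episode of severe hypoglycemia and no episode of DKA after randomization", with no limit tied to last dose. SAP 3.1.1 keeps this: "no episode of SH and no episode of DKA after randomization when used as an adjunct". SAP 6.8.1 narrows it to "no episode of SH and no episode of DKA from randomization to Week 24", uses the same span for the separate SH and DKA component proportions, and says events are assessed over the whole randomized 24-week period.

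**The rule that operates.** The same paragraph of SAP 6.8.1 refers to SAP 6.9.2 for event inclusion and summarizes it: "the cut-off date is the date of the last dose of double-blind study drug for SH events and 30 days after" last dose for DKA. SAP 6.9.2 confirms both halves: "For a hypoglycemic event, the date of the last dose of double-blind study drug will be the cut-off date" and "Other EOSIs, excluding hypoglycemic events, will be included in the analysis if the onset is within 30 days of last dose of study drug". SAP 6.8.6 uses the same rule for the net-benefit summaries ("the cut-off dates for their inclusion are defined in" 6.9.2). SAP 6.9.4 defines the treatment period for hypoglycemia as "including only those events that occur between date and time of first dose and date of last dose of double-blind study drug".

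**Early stoppers.** Protocol 6.3.3 has a patient who stops only the drug carry on with all study activities. Protocol 10.1 and SAP 2.3 assume 20% dropout, mainly patients who stop treatment but are followed to Week 24. SAP 5.2.1 imputes non-response only when the Week 24 observation is missing.

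**Sensitivity analyses (SAP 6.8.2).** There are three: the same analysis in the Per-protocol set, both events cut at last dose, and both events cut at last dose + 30 days.

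**The concern.** For an early stopper the two halves of the composite are measured over different periods. The A1C half uses the Week 24 value, taken off drug. The safety half stops at or shortly after last dose. A patient who stops at Week 8, has an adjudicated SH at Week 12 and reaches A1C below 7.0% at Week 24 counts as a responder, and also counts in the component table as free of SH to Week 24.

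The safety components are what make this a net-benefit endpoint (Protocol 3.6.2). If their label does not describe what was counted, and no planned analysis gives the to-Week-24 count, the report cannot show whether its conclusion holds for the endpoint as named. The counting window also depends on when each patient stops drug, which happens after randomization and may differ by arm.

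**Working it through.** **1. The gap in days.** Take 168 days on drug and the Week 24 target of Day 169 (SAP Table 5.1-1). Days before Week 24 that are not counted:

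| Drug stopped at | SH, primary | DKA, primary | Both, last dose + 30 analysis |
|---|---|---|---|
| Week 4 | 140 | 110 | 110 |
| Week 8 | 112 | 82 | 82 |
| Week 16 | 56 | 26 | 26 |
| Week 20 | 28 | 0 | 0 |

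The last dose + 30-day analysis reaches Week 24 only when last dose is on or after about Day 169 - 30 = 139. The last-dose analysis never does so for an early stopper. The Per-protocol set contains only treatment completers (SAP 4.4).

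**2. Planning figures.** The plan gives no figure for this gap. Its sample size reproduces: 0.55 vs 0.45, 90% power, two-sided 0.05, with continuity correction, gives 544 per group. The SH interval half-width also reproduces: 1.96 × √(2 × 0.10 × 0.90/700) + 1/700 = 0.033. Neither is affected.

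Inputs from SAP 2.3:
- SH at most 0.10.
- SH or DKA at most 0.15. With independence, DKA = 1 - 0.85/0.90 = 0.056.
- 20% stopping, which is 140 of 700 per arm and 280 in total.

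Assumptions of this check: constant hazards, and stopping times s uniform over 168 days. DKA after Week 24 is left out.

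**3. Event-free proportion among followed stoppers.** Daily hazards are SH = -ln(0.90)/168 = 0.000627 and DKA = -ln(0.85/0.90)/168 = 0.000340. Averaging over s:
- As named, both to day 168: 0.850
- Primary rule, mean of exp(-0.000627 s - 0.000340 min(s + 30, 168)): 0.914
- Both to last dose: 0.923
- Both to last dose + 30: 0.899

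The primary rule differs from the name by 0.91437 - 0.85000 = 0.06437, so about 6.4% of followed stoppers change event-free status. The last dose + 30 analysis still differs by 0.8987 - 0.8500 = 0.0487, which is about three quarters of the gap.

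**4. Effect on the composite.** Let d be the stopping fraction and r the stoppers' A1C response, for sotagliflozin (S) and placebo (P), and f the share of stoppers with a Week 24 A1C.
- Patients changed = 700 × 0.06437 × f × (d_S r_S + d_P r_P)
- Shift in difference = 0.06437 × f × (d_S r_S - d_P r_P)

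Under SAP 2.3 (equal event rates, 20% stopping applied to both arms, sotagliflozin stoppers responding as placebo) the bracket in the second formula is zero, so the shift is zero.

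The documents give no placebo A1C rate, so two assumed pairs are shown. The second takes the plan's 0.15 A1C difference around its pooled 0.50. Stopping is 20/20, 25/15 or 15/25 (sotagliflozin/placebo, %). Sotagliflozin stoppers respond at either arm's rate.

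| A1C response | Patients changed of 1400 | Lowest shift | Highest shift |
|---|---|---|---|
| 35% vs 25% | 2.3 (f = 0.5) to 5.6 (f = 1) | 0.06437 × (0.15 - 0.25) × 0.25 = -0.0016 | 0.06437 × (0.25 × 0.35 - 0.15 × 0.25) = +0.0032 |
| 57.5% vs 42.5% | 7.7 to 9.4 (f = 1) | 0.06437 × (0.15 - 0.25) × 0.425 = -0.0027 | 0.06437 × (0.25 × 0.575 - 0.15 × 0.425) = +0.0051 |

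For scale, take composite rates of 0.85 times the A1C rates at 700 per arm. The standard error is then √(0.2975 × 0.7025/700 + 0.2125 × 0.7875/700) = 0.023 for the first pair and 0.026 for the second. The largest shifts are about 14% and 20% of one standard error.

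**5. Components.** If all 280 stoppers are followed:
- SH uncounted: 280 × (0.9491 - 0.9000) = 13.8 patients, so the table shows 9.0% instead of 10.0%. About 4.5 fall within 30 days of last dose and 9.2 later.
- DKA uncounted: 280 × (0.9629 - 0.9444) = 5.2 patients, so 5.2% instead of 5.6%.

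**6. Lower rates (illustrative: SH 5%, union 8%).** Status changes in 0.9544 - 0.9200 = 3.4% of followed stoppers. One to three patients change responder status at 35%/25%, and about 7 SH and 3 DKA patients go uncounted.

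**The case against.** The cut-offs are not hidden. SAP 6.8.1 states them beside the endpoint, and Section 7 reports two added analyses using one common cut-off, which implies that the primary cut-offs differ. Counting safety events close to exposure is a legitimate choice, and the DKA limit equals the capture window for events of special interest in Protocol 9.5. Captured post-dose events stay visible: SAP 6.9.2 plans by-patient listings and a summary from last dose to last dose + 30 days, and SAP 6.9.4 plans follow-up summaries and listings of adjudicated SH. Events never captured cannot be recovered by a new analysis. The effect is small, and zero under the planning assumptions.

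Most of this stands. It rules out calling the primary rule an error in itself, and it limits the harm. It does not make the label correct: a to-Week-24 name remains on a count that ends earlier. Listings are not a to-Week-24 composite. Section 7 lists the added analyses but does not record the last-dose SH cut-off as a change from the protocol.

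**Conclusion.** The point holds as a mismatch between the named and the counted endpoint, confined to early stoppers who remain in follow-up. It should be fixed before unblinding, but it does not threaten the trial's conclusion. The sizes rest on constant hazards, uniform stopping, planning upper bounds for event rates, and assumed A1C rates and stopping imbalances. They are illustrations, not bounds.

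A reader might infer more than the documents support:
- *That no analysis reaches Week 24 for any early stopper.* The last dose + 30-day analysis does for those stopping in the final 30 days, 30/168 = 18% under uniform stopping.
- *That the result is tilted toward sotagliflozin.* The sign depends on which arm stops more and how stoppers respond. The documents fix neither.
- *That the A1C reduction ≥0.5% without SH endpoint (SAP 6.8.4.5) is mislabeled in the same way.* That section cites no cut-off, and SAP 6.8.4 says post-discontinuation observations are used. Set against SAP 6.9.2, the window is unclear rather than shown to be wrong.
- *That the primary analysis must change.* Capture is written to end 30 days after last dose, so a to-Week-24 primary could rest on incomplete data.

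DKA counted after Week 24 in completers is a separate, smaller matter that fits the protocol wording and is not part of this point.

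**What to change.** Before unblinding:
1. Add a named sensitivity analysis of the primary endpoint that counts positively adjudicated SH and DKA from randomization to a fixed Week 24 date regardless of drug status. Day 169 or the date of the Week 24 A1C would serve. A fixed date is needed because the Week 24 window in SAP Table 5.1-1 starts at Day 142 and has no upper limit.
2. Keep the SAP 6.9.2 cut-offs as primary if they are intended, but reword the endpoint and its SH and DKA components in SAP 6.8.1 to state them.
3. In SAP Section 7, list the last-dose SH cut-off as a change, and state the DKA cut-off, noting that it matches the protocol's capture window.
4. Say which window applies to SH in SAP 6.8.4.5.
5. Reconcile the capture window (Protocol 9.5, SAP 6.9.2) with continued follow-up (Protocol 6.3.3), and report that events beyond last dose + 30 days may be incompletely captured.

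Cost: one date rule, one extra analysis and label edits, with no new visits. Some site queries and blinded adjudication may be needed. At the upper-bound rates about 9 of the 14 uncounted SH patients, and all 5 uncounted DKA patients, lie beyond the written capture window, so the added analysis may be incomplete for them.
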